### 10.5.2 Secondary Efficacy Analyses

- The change of FPG level from baseline at Week 12 will be summarized with mean, standard deviation, median, 25th & 75th percentiles, minimum, and maximum, overall and by each of the four groups, separately. To identify statistically significant difference in the change of FPG level from baseline at Week 12 between the four groups, one-way ANOVA will be performed. The tests between the experimental groups and the control group will be performed using Dunnett's test. If the change variables are markedly non-normally distributed then Kruskal-Wallis test and Wilcoxon rank-sum test will be used respectively. Specifically, all three experimental groups will be compared to the control group on the change: Dose A vs. D, B vs. D, and C vs. D. Also, to identify statistical significant difference between baseline and Week 12, one-sample t-test (paired t-test) or Wilcoxon signed-rank test will be performed within each of the four groups.
- The proportion of subjects achieving HbA1c goal of < 7.0% at Week 12 will be summarized with count and percentage, overall and by each of the four groups, separately. The proportion of subjects achieving HbA1c goal of < 7.0% at Week 12 will be compared for the experimental groups versus the control group using chi-square test method. In a case when the expected cell frequencies are less than 5 in >20%, Fisher's exact test will be used.
- The proportion of subjects achieving HbA1c goal of < 6.5% at Week 12 will be summarized with count and percentage, overall and by each of the four groups, separately. The proportion of subjects achieving HbA1c goal of < 6.5% at Week 12 will be compared for the experimental groups versus the control group using chi-square test method. In a case when the expected cell frequencies are less than 5 in >20%, Fisher's exact test will be used.
- The change in waist circumference from baseline at Week 12 will be summarized with mean, standard deviation, median, 25th & 75th percentiles, minimum, and maximum, overall and by each of the four groups, separately. To identify statistically significant difference in the change in waist circumference from baseline at Week 12 between the four groups, one-way ANOVA will be performed. The tests between the experimental groups and the control group will be performed using Dunnett's test. If the change variables are markedly non-normally distributed then Kruskal-Wallis test and Wilcoxon rank-sum test will be used respectively. Specifically, all three experimental groups will be compared to the control group on the change: Dose A vs. D, B vs. D, and C vs. D. Also, to identify statistical significant difference between baseline and Week 12, one-sample t-test (paired t-test) or Wilcoxon signed-rank test will be performed within each of the four groups.
- The change of postprandial (2 hours after dinner) blood glucose level from baseline at Week 12 will be summarized with mean, standard deviation, median, 25th & 75th percentiles, minimum, and maximum, overall and by each of the four groups, separately. To identify statistically significant difference in the change of postprandial (2 hours after dinner) blood glucose level from baseline at Week 12 between the four groups, one-way ANOVA will be performed. The tests between the experimental groups and the control group will be performed using Dunnett's test. If the change variables are markedly non-normally distributed then Kruskal-Wallis test and Wilcoxon rank-sum test will be used respectively. Specifically,

all three experimental groups will be compared to the control group on the change: Dose A vs. D, B vs. D, and C vs. D. Also, to identify statistical significant difference between baseline and Week 12, one-sample t-test (paired t-test) or Wilcoxon signed-rank test will be performed within each of the four groups.

- The change of OGTT from baseline at Week 12 will be summarized with mean, standard deviation, median, 25th & 75th percentiles, minimum, and maximum, overall and by each of the four groups, separately. To identify statistically significant difference in the change of OGTT from baseline at Week 12 between the four groups, one-way ANOVA will be performed. The tests between the experimental groups and the control group will be performed using Dunnett's test. If the change variables are markedly non-normally distributed then Kruskal-Wallis test and Wilcoxon rank-sum test will be used respectively. Specifically, all three experimental groups will be compared to the control group on the change: Dose A vs. D, B vs. D, and C vs. D. Also, to identify statistical significant difference between baseline and Week 12, one-sample t-test (paired t-test) or Wilcoxon signed-rank test will be performed within each of the four groups.
- The change of score in ADDQoL questionnaire from baseline at Week 12 will be summarized with mean, standard deviation, median, 25th & 75th percentiles, minimum, and maximum, overall and by each of the four groups, separately. To identify statistically significant difference in the change of score in ADDQoL questionnaire from baseline at Week 12 between the four groups, one-way ANOVA will be performed. The tests between the experimental groups and the control group will be performed using Dunnett's test. If the change variables are markedly non-normally distributed then Kruskal-Wallis test and Wilcoxon rank-sum test will be used respectively. Specifically, all three experimental groups will be compared to the control group on the change: Dose A vs. D, B vs. D, and C vs. D. Also, to identify statistical significant difference between baseline and Week 12, one-sample t-test (paired t-test) or Wilcoxon signed-rank test will be performed within each of the four groups.
- Sensitivity analysis described below will be performed for the secondary endpoints at Week 12:
  1. Summary statistics and ANOVA model for continuous endpoints using imputed data by LOCF, EAS.
  2. Primary summary and analysis method based on Per Protocol Set.

### 10.5.3 Exploratory Efficacy Analyses

The exploratory efficacy variables will be summarized with mean, standard deviation, median, 25th & 75th percentiles, minimum, and maximum, overall and by each of the four groups, separately. To identify statistically significant difference in the exploratory efficacy variables between the four groups, one-way ANOVA will be performed. The tests between the experimental groups and the control group will be performed using Dunnett's test. If the change variables are markedly non-normally distributed then Kruskal-Wallis test and Wilcoxon rank-sum test will be used respectively. Specifically, all three experimental groups will be compared to the control group on the change: Dose A vs. D, B vs. D, and C vs. D. Also, to identify statistical significant difference between baseline and Week 12, one-sample t-test (paired t-test) or Wilcoxon signed-rank test will be performed within each of the four groups.

- Thyroid Function Test: TSH, T3, and T4
  - Serum Parameters: zinc, insulin, adiponectin, C-peptide, leptin, and glucagon
  - Urine Parameters: zinc, glucose, microalbumin, and copper
  - TAFGC
  - BMI
- Sensitivity analysis described below will be performed for the exploratory endpoints at Week 12:
1. Primary summary and analysis method based on Per Protocol Set.

## 10.6 Safety Analyses

Safety analysis will be performed based on data of safety analysis set. Safety variables will be summarized with descriptive statistics, overall and by each of the four groups, separately. Continuous safety variables will be summarized with mean, standard deviation, median, 25th & 75th percentiles, minimum, and maximum. Categorical safety variables will be summarized with count and percentage.

**No statistical testing comparing treatment groups will be performed in the safety analyses.**

### 10.6.1 Adverse Events

- All adverse events (AEs) in CRF will be classified by SOC and PT according to MedDRA version 20.0.
- A treatment-emergent AE (TEAE) will be defined as an AE that began or worsened on or after the first treatment dose. AEs recorded prior to the first application of study treatment will be considered non-treatment-emergent. AEs with insufficient date or time information to determine whether or not they were treatment-emergent will be considered treatment-emergent.
- All reported AEs (treatment-emergent or not) will be listed. Only TEAEs will be summarized.
  - (1) TEAEs will be summarized with the number of subjects who have AEs, incidence rate of AEs, and the number of AEs by categorizing as follows;
    - ① AE/ADR\* (Adverse event/Adverse drug reaction)  
\*TEAEs which have the relationship to investigational product as 'Definite', 'Probable', and 'Possible' are regarded as Drug-Related Adverse Events (ADR).
    - ② SAE/SADR (Serious adverse event/Serious adverse drug reaction)
  - (2) TEAEs will also be summarized with the number of subjects who have AEs, incidence rate of AEs, the number of AEs, and its percentage by categorizing as follows.
    - ① Outcome
      - Recovered or Resolved
      - Recovering or Resolving
      - Recovered or Resolved with Sequelae
      - Not Recovered or Not Resolved

- Death Related to Adverse Event
  - Unknown
  - ② Severity
    - Mild
    - Moderate
    - Severe
  - ③ Relationship to Investigational Product (IP)
    - Definite
    - Probable
    - Possible
    - Not Likely
    - Not Related
  - ④ Action Taken Regarding IP
    - None
    - Reduced
    - Increased
    - Interrupted
    - Discontinued
  - ⑤ Treatment Required
    - Yes
    - No
  - ⑥ Seriousness
    - Is life-threatening
    - Requires in-patient hospitalization or prolongation of existing hospitalization
    - Results in persistent or significant disability or incapacity
    - Is a congenital anomaly or birth defect
    - Is an important medical event
    - Results in death
- Episodes of hypoglycemia and hyperglycemia (V2-V8)
    - (1) Hypoglycemia occurred after previous visit will be summarized with the number of subjects who are occurred episode and the count of episode by each visit separately.
    - (2) Hyperglycemia occurred after previous visit will be summarized with the number of subjects who are occurred episode and the count of episode by each visit separately.
    - (3) Sponsor defined Hypoglycemia (blood glucose  $\leq 70$  mg/dL) occurred after previous visit will be summarized with the number of subjects who are occurred episode and the count of episode by each visit separately.

- (4) Sponsor defined Hyperglycemia (blood glucose  $\geq$  180 mg/dL) occurred after previous visit will be summarized with the number of subjects who are occurred episode and the count of episode by each visit separately.

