### **4.2 Selection of Study Population**

#### **4.2.1 Inclusion Criteria**

To be enrolled in the study, a subject must meet all of the following criteria:

1. Males or females aged 18 or older.
2. Subjects diagnosed with type 2 diabetes mellitus according to the American Diabetes Association (ADA) criteria.
3. Subjects treated with stable doses of insulin and/or other hypoglycemic agent(s) for type 2 diabetes mellitus for at least 2 months prior to randomization.
4. Subjects whose fasting blood glucose levels are reasonably stable for at least 2 months prior to randomization and during the 2-week screening period. Stable glucose levels are defined based on the fact that the study subjects did not change the dose and/or type of insulin injection and/or other hypoglycemic agent(s) during the last 2 months and during the 2-week screening period to adjust blood glucose.
5. Subjects who have Hemoglobin A1c levels of 7.5 to 10.0 % at Screening.

6. Subjects whose BMI is 30 or above.
7. Subjects who can give written informed consent.

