At the same time, hyperglycemia will be well maintained by examining subjects bi-weekly. Taking Cyclo-Z may increase fasting blood glucose initially for 2 months due to the reduction in pancreatic insulin secretion, which could occur with improved insulin sensitivity. Subjects will be instructed to monitor for increased thirst, urination and blurry vision, but subjects will also be advised that the best method for detecting hyperglycemia is by measuring blood glucose level.

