**< How to fill out this diary >**

- Please record this diary everyday starting the evening of the day it's dispensed until the morning of your next visit to the hospital.
- Return this diary to the person in charge of this study at your next visit. You will receive a new diary at each visit.
- Study Site: This is the name of the hospital you will be visiting for the study.
- Date Dispensed: This is the date you received this diary. Please record it in the format of DD/MMM/YYYY (Example: 03 Feb 2015).
- Date: This is the date you checked your blood sugar levels and took the study medication. Please record it in the format of DD/MMM/YYYY (Example: 03 Feb 2015).
- Blood Sugar: Please check the unit in which your blood sugar level is measured.
- Fasting before breakfast: Write down your blood sugar level tested in a fasted state before breakfast.
- 2 hours after dinner: Write down your blood sugar level tested 2 hours after dinner.
- Not done: If you did not check your blood sugar, please check the box and state the reason.
- Study Medication: Please check whether you took the study medication or not. On the evening before your visit to the hospital, indicate when you took study medication in a 24 hour format (Example: 6:00 pm = 18:00, 8:00 pm = 20:00).
- Not taken: If you did not take your study medication, please check the box and state the reason.
- If you are unable to return to the study site 14 days after your previous visit, use the additional rows provided to continue recording your blood sugar levels and the study medication compliance until your next visit.
- Comments: Please leave any comments, questions or concerns you may have. Also inform the study staff of any changes to your diet or exercise regimen.
- Diary return date and confirmation signature: Please record the date the diary is returned to the site and your signature to confirm.

*If you have any further questions or problems about filling out the diary or the study in general, please contact your clinical site.*

Date Dispensed		(Example: 03 Feb 2015)	
Day	Date (DD/MMM/YYYY)	Blood Sugar (  mg/dl  mmol/L)	
1		Fasting before breakfast	2 hours after dinner
		N/A	
		 Not done (reason: )	
Study Medication:  Taken  Not taken (reason: )			
2		Fasting before breakfast	2 hours after dinner
		 Not done (reason: )	

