#### **Appendix 4: Determining Hypoglycemic and Hyperglycemic Episodes**

For this study, a subject will be described as having hypoglycemic or hyperglycemic episodes when the following definitions are met:

- Documented Symptomatic Hypoglycemia is defined as an event during which typical symptoms of hypoglycemia are accompanied by a measured plasma glucose concentration  $\leq 70$  mg/dl.
- Asymptomatic Hypoglycemia is defined as an event not accompanied by typical symptoms of hypoglycemia but with a measured plasma glucose concentration  $\leq 70$  mg/dl.
- Probable symptomatic hypoglycemia is defined as an event during which symptoms of hypoglycemia are not accompanied by a plasma glucose determination, but that was presumably caused by a plasma glucose concentration  $\leq 70$  mg/dl.
- Relative Hypoglycemia is defined as an event during which the person with diabetes reports of the typical symptoms of hypoglycemia, and interprets those as indicative of hypoglycemia, but with a measured plasma glucose concentration  $> 70$  mg/dl.
- Severe Hypoglycemia is defined as an event requiring assistance of another person to actively administer carbohydrate, glucagons, or other resuscitative actions, or when a measured plasma glucose concentration is  $< 40$  mg/dl.
- Hyperglycemia is defined as plasma glucose level  $> 140$  mg/dl.
- Severe hyperglycemia is defined as plasma glucose level  $> 300$  mg/dl.

\* *Definitions of hypoglycemic episodes were defined per "Defining and Reporting Hypoglycemia: A report from the American Diabetes Association Workgroup on Hypoglycemia" from May, 2005 issue of Diabetes Care.*

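### If hyperglycaemia episodes come from the daily log, the >140 mg/dl subject count sits near its ceiling in every arm, and the episode counts have no denominator of readings or time

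*SAP*

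**What the plan says.** Episodes of hypoglycaemia and hyperglycaemia are a named safety endpoint (Protocol 3.3, SAP 4.4), assessed at Visits 2 to 8.

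- **Definition in the protocol.** Appendix 4: "Hyperglycemia is defined as plasma glucose level" above 140 mg/dl. It makes no fasting/post-meal distinction and has no rule for when several high readings form one episode. It adds "Severe hyperglycemia is defined as plasma glucose level" above 300 mg/dl, for which the SAP plans no separate table.
- **Output in the SAP.** 10.6.1 item (2): "Hyperglycemia occurred after previous visit will be summarized with the number of subjects who are occurred episode and the count of episode", by visit, with no cut-off restated. Item (4) gives the same two statistics for "Sponsor defined Hyperglycemia (blood glucose" at or above 180 mg/dL). SAP 10.6 adds "Categorical safety variables will be summarized with count and percentage", which gives a percentage of subjects but no rate per reading or per unit of time.
- **Population.** Protocol 4.2.1: "Subjects who have Hemoglobin A1c levels of 7.5 to 10.0 % at Screening".
- **Readings.** Two a day, before breakfast and 2 hours after dinner (Protocol 4.1). The diary instructions allow gaps: "Not done: If you did not check your blood sugar, please check the box and state the reason".
- **Why a rise is of interest.** Protocol 5.8: "Taking Cyclo-Z may increase fasting blood glucose initially for 2 months".

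**The concern.** A subject with type 2 diabetes and an HbA1c of 7.5-10.0% who takes some 28 readings in two weeks, half of them after dinner, will almost certainly have one above 140 mg/dl whatever the treatment. A statistic that placebo already fills cannot move.

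The episode count can move, but it also grows with the number of readings. That number varies with log completion, with visit windows and with early withdrawal. Protocol 9.5 ends participation when glucose stays high after two weeks, so subjects with the most hyperglycaemia may stop contributing readings. The pre-dose count at Visit 2 is not a clean reference either: Protocol 6.2.1 allows that visit up to 7 days late, so the run-in log spans 14 to 21 days (28 to 42 readings).

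At stake is whether the table can be read. Safety data are descriptive only, so readers will compare these numbers by eye.

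**Working it through.** The documents state no expected rate or count for hyperglycaemia episodes, so there is no plan figure to reproduce.

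**Inputs from the documents.** Cut-offs >140 mg/dl (Protocol Appendix 4) and ≥180 mg/dL (SAP 10.6.1); 2 readings a day; intervals of 14 ± 3 days (Protocol 6.2.2), so 2 × 11 = 22 to 2 × 17 = 34 readings, nominally 28; 16 subjects per arm.

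**Inputs assumed (not in the documents).** Subject mean glucose 140, 160 or 180 mg/dl, with fasting 10 below and post-dinner 20 above it; between-subject SD 20 or 30; within-subject SD 25 or 35; normal, independent readings; any logged reading above the cut-off counts as an episode.

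**Step 1: saturation without a glucose model.** If a share p of a subject's readings exceeds the cut-off, P(at least one in n) = 1 − (1 − p)^n. With n = 28:

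- p = 5%: 76%
- p = 10%: 1 − 0.9^28 = 94.8%, or 0.948 × 16 = 15.2 of 16 subjects
- p = 20%: 99.8%

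For 95% of subjects to qualify, p need only be 1 − 0.05^(1/28) = 10.1% (12.7% with 22 readings, 8.4% with 34).

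**Step 2: subjects with an episode, under the glucose model.** P = 1 − [(1 − p_fasting)(1 − p_dinner)]^14, averaged over subject means. The rise is added to every reading.

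| Cut-off | No rise | +30 mg/dl | Lowest case, subjects of 16 |
|---|---|---|---|
| >140 | 97-100% | 99.8-100% | 15.6 → 16.0 |
| ≥180 | 76-100% | 95-100% | 12.1 → 15.2 |

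A low-glucose check: a subject averaging 110 fasting and 130 post-dinner with SD 20 has p_fasting = 0.067 and p_dinner = 0.309, so P(>140) = 1 − (0.933 × 0.691)^14 = 99.8%. At ≥180 a subject averaging 110 and 140 with SD 20 reaches only 28%.

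**Step 3: episode count.** Expected count = 14 × (p_fasting + p_dinner). The share of readings that must be lost to cancel the rise is 1 − count(0)/count(+30). At mean 160:

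- >140: 19.5-21.2 rises to 24.4-26.3, about +25%. Cancelled by 1 − 21.23/26.32 = 19% to 1 − 19.49/24.39 = 20% fewer readings.
- ≥180: 9.4-10.6 rises to 17.4-18.6, +64% to +97%. Cancelled by 1 − 10.59/17.38 = 39% to 1 − 9.42/18.55 = 49% fewer readings.

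At mean 180, 9-12% fewer readings suffices at >140. Across means 140-180, cancelling at ≥180 takes about 29-64%.

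**Step 4: a rise in fasting readings only, with unequal completion.** Separate assumed scenario: fasting mean 155, post-dinner 30 higher, both SDs 30, cut-off >140. At 90% completion an arm of 16 has 16 × 28 × 0.9 = 403 readings; at 70% it has 314.

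| Arm | Completion | Fasting rise | Episodes | % of readings |
|---|---|---|---|---|
| Placebo | 90% | 0 | 301 | 301/403 = 75% |
| Active | 90% | +20 | 333 | 333/403 = 83% |
| Active | 70% | +20 | 259 | 259/314 = 83% |
| Active | 70% | 0 | 234 | 234/314 = 75% |

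With equal completion the raw count shows the rise (301 v 333). With unequal completion it points the wrong way (301 v 259), and it suggests a benefit where there is none (301 v 234). The percentage of readings is right in all three comparisons.

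**The case against.** A reader might infer that this endpoint cannot show a glucose rise the protocol expects, and that the table would read alike in all arms whatever the drug does. The documents do not support that.

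- The SAP plans two statistics, and only the subject count saturates. With similar completion the episode count rises, clearly so at ≥180.
- The ≥180 subject share can also move, from 76% to 95% in the lowest case.
- Protocol 5.8 says fasting glucose may increase; it neither predicts a rise nor gives its size.
- FPG at Weeks 0, 4, 8 and 12 and chemistry glucose are summarised by visit, and the post-dinner log is analysed as a two-week mean, which does not grow with the number of readings.

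These points stand and limit the concern. The cover is still partial: blood draws during treatment come only at Weeks 4, 8 and 12, and no planned analysis outside the episode tables uses the daily fasting log.

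It can also be said that completion has no reason to differ by arm in a blinded trial whose logs are reviewed at every visit. Similar gaps in all arms would indeed not hide a difference. But with 16 per arm chance imbalance is possible, and termination for persistently high glucose ties observation time to the outcome.

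Finally, use of any diary reading is an inference. The visit procedures list episode assessment apart from log review, Appendix 4 speaks of plasma glucose and item (4) of blood glucose, and the SAP names no source. If sites record episodes by another route, the 28-reading arithmetic does not describe item (2). That gap itself needs closing.

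**Conclusion.** The point holds in a limited form. If the log feeds the tables, the >140 subject count is uninformative: 97-100% without a drug effect against 99.8-100% after a 30 mg/dl rise, less than half a subject in 16. The ≥180 subject count is less saturated. The episode counts respond to glucose but are open to confounding by the number of readings. At mean 160, about 20% fewer readings cancels a 30 mg/dl rise at >140, and 39-49% fewer at ≥180; a large enough imbalance reverses the direction.

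The sizes rest on assumed glucose means and SDs and on independent readings. Near-saturation at 140 holds over the whole range tried; the ≥180 results depend strongly on the glucose level. The table is descriptive, in a trial not sized on power, and no decision rule depends on it. This is therefore a cheap improvement in interpretability and does not invalidate the safety analysis.

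**What to change.** In SAP 10.6.1, items (2) and (4):

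1. State which readings feed each table (log, site blood draws, OGTT, or episodes recorded by the site) and what counts as one episode.
2. Label the Appendix 4 definition (>140 mg/dl) and the sponsor definition (≥180 mg/dL) separately, so that the two are reconciled and each table shows which it uses.
3. Beside the planned outputs, add per subject and interval the percentage of logged readings above each of these two cut-offs, fasting and post-dinner separately, with the number of logged readings as denominator.
4. Summarise these percentages by arm and visit, with change from the run-in log reviewed at Visit 2.

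Leave the clinical definitions and the actions in Protocol 9.5 as they are. The cost is SAP wording, one derived variable from data already collected, and one more descriptive table.
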